8.3 TIME PERIOD AND FREQUENCY FOR EVENT ASSESSMENT AND FOLLOW-UP

The occurrence of an AE or SAE may come to the attention of study personnel during study visits and interviews of a study participant presenting for medical care, or upon review by a study monitor. All AEs including local and systemic reactions not meeting the criteria for SAEs will be captured on the appropriate RF. Information to be collected includes event description, time of onset, clinician's assessment of severity, relationship to study product (assessed only by those with the training and authority to make a diagnosis), and time of resolution/stabilization of the event. All AEs occurring while on study must be documented appropriately regardless of relationship. All AEs will be followed to adequate resolution.

Any medical condition that is present at the time that the participant is screened will be considered as baseline and not reported as an AE. However, if the study participant's condition deteriorates at any time during the study, it will be recorded as an AE. UPs will be recorded in the data collection system throughout the study.

Changes in the severity of an AE will be documented to allow an assessment of the duration of the event at each level of severity to be performed. AEs characterized as intermittent require documentation of onset and duration of each episode.

The PI will record all reportable events with start dates occurring any time after informed consent is obtained until 7 days after the last day of study participation. At each study visit/followup phone visit, the investigator will inquire about the occurrence of AE/SAEs since the last visit. Events will be followed for outcome information until resolution or stabilization.

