10.2 STATISTICAL HYPOTHESES

No statistical hypothesis

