10.3 ANALYSIS DATASETS

Per protocol analysis

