10.4 DESCRIPTION OF STATISTICAL METHODS

10.4.1 GENERAL APPROACH

Categorical data descriptive statistics will be presented as percentages, while continuous data descriptive statistics will be presented with the mean and standard deviation. Due to our goal of establishing estimates of centrality and spread for various measures to be used in future studies, no inferential tests will take place in this study.

Version 01.2 Protocol:201607761 Version 20.2 Version 01.2

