10.4.3 ANALYSIS OF THE SECONDARY ENDPOINT(S)

Observations with missing data are dropped from those analyses involving data variable.

Change in mood score using PHQ-9 score

This will be analyzed as the difference in PHQ-9 scores from baseline to final measurement between drug and placebo. The mean and standard deviation estimates of the differences will be provided.

Change in minute ventilation during HCVR testing:

This will be analyzed as the difference in minute ventilation during HCVR testing from baseline to final measurement between drug and placebo. The mean and standard deviation estimates of the differences will be provided.

Change in slope of HCVR

This will be analyzed as the difference in slope of HCVR between drug and placebo. Using a linear mixed model, we will include a predictor that is the interaction between HCVR slope and the treatment group. The mean and standard deviation estimates of the differences will be provided.

Difference in duration of abnormal breathing during periotal period:

Mean duration of abnormal breathing during perictal periods between drug and placebo will be compared. The mean and standard deviation estimates of the differences will be provided.

Difference in oxygen saturation during periotal period

Mean drop in oxygen saturation during perictal period between drug and placebo will be compared. The mean and standard deviation estimates of the differences will be provided.

Difference in CO₂ level in periotal period

Mean change in CO₂ level in periocal period compared to pre seizure baseline will be compared between drug and placebo. The mean and standard deviation estimates of the differences will be provided.

All the secondary outcome measures will be estimated using generalized linear mixed models (GLMMs), specifying an identity link for normally distributed data and the log link for right-skewed data.

Since we are interested in obtaining estimates for future studies, we will not run non-parametric analyses, which only provide p-values.

Version 01.2 Protocol:201607761 Version 20.2 Version 01.2

Assessment of adverse events

All the adverse events will be recorded. Frequency of each adverse events will be compared between the two groups and tested using one tail t-test with type I error at 0.025

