10.4.4 SAFETY ANALYSES

All the adverse events will be recorded. Severity and relationship to intervention will be determined as described in section 8. Frequency of each adverse events will be compared between the two groups and tested using one tail t-test with type I error at 0.025.

Adverse events leading to premature discontinuation from the study drug and serious treatment-emergent AEs should be presented either in a table.

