10.4.6 BASELINE DESCRIPTIVE STATISTICS

We plan to compare the baseline descriptive statistics between the treatment and control groups and establish if there is a significant difference of any variables. For continuous variables, a two sample t-test will be used to compare data that appear to be normally distributed (Wilcoxon Rank Sum test for skewed data). For categorical data, Pearson's Chi-square test of independence will be used.

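### The plan rules out inferential tests but orders t-tests on each adverse event and tests at baseline, and the adverse-event comparison has no safety set and no counting unit.

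*Combined protocol and SAP*

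**What the plan says.** All references are to the combined protocol and SAP.

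- **Section 10.2** reads "No statistical hypothesis". **Section 10.4.1** says, of the whole study, that "no inferential tests will take place in this study", because the aim is to obtain estimates for later trials.
- **Section 10.4.4** says of AEs: "Frequency of each adverse events will be compared between the two groups and tested using one tail t-test with type I error at 0.025". **Section 10.4.3** repeats the instruction: "tested using one tail t-test with type I error at 0.025". It then asks for a table of serious AEs and of AEs leading to discontinuation.
- **Section 10.4.6** compares the arms at baseline to "establish if there is a significant difference of any variables". It uses a t-test or Wilcoxon test for continuous variables, and for categorical ones "Chi-square test of independence will be used".
- **Section 10.3**, on analysis datasets, consists of "Per protocol analysis". No safety set is named.
- **Section 8.3** says "AEs characterized as intermittent require documentation of onset and duration of each episode".
- **Section 5.4.2** takes participants with a serious AE off the study and follows the event to resolution. For withdrawal after randomisation it plans attempted phone contact for safety only. Section 7.3.5 has no early termination visit.

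**The concern.** A statistician cannot carry out both 10.4.1 and 10.4.4. A comparison with a stated type I error is an inferential test, and 10.4.1 exempts neither safety nor baseline.

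If the AE comparison is done, two choices that shape its result are not fixed.

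- **Who is counted.** The one named set is per protocol. A participant terminated for a serious AE is unlikely to belong to it, so membership can depend on the outcome being compared.
- **What is counted.** Both participants with an event and episodes of an event will be on file, and frequency could mean either.

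Both choices could then be made after the data are seen. The trial exists to supply estimates for future studies (section 10.1), and an AE rate with no defined unit or denominator is hard to reuse. The direction of the single tail is also not written down. That is one missing phrase with an obvious natural reading, drug worse than placebo.

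**Working it through.** The plan gives no expected AE rate, power or sample-size basis, so there is no figure of its own to reproduce. The only stated number for the AE test is the level, 0.025 one-tailed.

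**1. The sections side by side.** Section 10.4.1 excludes inferential tests from the study. Sections 10.4.3 and 10.4.4 require one for each AE, and section 10.4.6 requires one for each baseline variable. No text limits 10.4.1 to efficacy or lists exceptions, so following either instruction breaks the other.

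**2. Does the counting unit matter?** Inputs: 20 per arm (section 5.3, and 40 randomised 1:1 in the Protocol Summary). The event counts are assumed. The pooled t statistic is t = (m1 − m2) / √(s² × 2/20), with s² = (SS1 + SS2)/38 and 38 degrees of freedom. Placebo has no events, so m2 = 0 and SS2 = 0.

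- *Participants, 4 v 0.* m1 = 4/20 = 0.20. SS1 = 4 − 4²/20 = 3.20. s² = 3.20/38 = 0.0842. Standard error = √(0.0842 × 0.1) = 0.0918. t = 0.20/0.0918 = 2.18, one-sided p = 0.018.
- *Episodes, the same four people with 6, 1, 1 and 1.* m1 = 9/20 = 0.45. SS1 = 36 + 1 + 1 + 1 − 9²/20 = 34.95. s² = 34.95/38 = 0.9197. Standard error = √(0.9197 × 0.1) = 0.3033. t = 0.45/0.3033 = 1.48, one-sided p = 0.073.

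The same people and events fall on opposite sides of 0.025. The effect comes from uneven repeats. If every affected participant had the same number of episodes and the other arm had none, the data would only be rescaled and p would not change.

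**3. Does the denominator matter?** All counts are assumed, since the documents give none. Suppose 3 of 20 fluoxetine completers and 1 of 20 placebo completers had a given AE, and three further participants were terminated with that AE.

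| Who is counted | Fluoxetine | Placebo | Difference |
|---|---|---|---|
| Completers only | 3/20 = 15.0% | 1/20 = 5.0% | 10.0 points |
| Plus three terminated on fluoxetine | 6/23 = 26.1% | 1/20 = 5.0% | 21.1 points |
| Plus three terminated on placebo | 3/20 = 15.0% | 4/23 = 17.4% | −2.4 points |

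The last row is the mirror case (1 + 3 = 4 events, 20 + 3 = 23 people). A completers-only denominator can therefore understate or overstate the contrast, and the direction cannot be known in advance.

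**4. What depends on these tests?** The primary endpoints (section 10.4.2) are recruitment and retention counts and percentages. The halting rule (section 8.5) counts individual severe AEs judged probably related. Neither uses a p-value.

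**The case against.** **Consequences are small.** This is a feasibility pilot, no decision rests on the AE or baseline p-values, and 10.4.4 tabulates serious AEs and those leading to discontinuation. This stands, and it limits the weight of the point. A reader might infer that terminated participants' serious events vanish from the report; because of that table, they do not. What lacks a sound denominator is the comparison between arms.

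**The denominator is stated.** Section 10.3 can be read as making it per protocol. That is fair as a literal reading, but the set is undefined and selects on the outcome. Section 5.4.1 words termination after a serious AE as something the investigator may do, while 5.4.2 words it as something that will happen. Those passages need reconciling, and how many participants the set loses depends on the answer.

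**The choice of a t-test implies a count.** It does not settle the unit. The plan's own rule for baseline data sends categorical variables to chi-square and skewed ones to Wilcoxon, so neither 0/1 indicators nor typical episode counts point clearly to a t-test.

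**Stronger readings.** A reader might infer that a t-test on 0/1 data gives badly wrong p-values. Enumerating all 21 × 21 tables at 20 per arm, with the tail fixed as drug worse, the actual error at nominal 0.025 is 0.006, 0.019, 0.025 and 0.027 for true rates of 5%, 10%, 20% and 30%. Accuracy is not the complaint. A reader might also infer that the tail would be picked after the fact; nothing in the documents suggests it. Nor do the model-based comparisons in 4.2.3 and 10.4.3 fall under this point: they can be reported as estimates without a test.

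**Conclusion.** The point holds. Sections 10.2 and 10.4.1 cannot be followed together with 10.4.3, 10.4.4 and 10.4.6, and the plan states no exception. The AE comparison also lacks a safety set and a defined counting unit. In the examples, the unit moves p from 0.018 to 0.073, and three terminated participants move a 10-point difference to 21 points or to about −2 points, depending on their arm. These sizes rest on assumed counts at 20 per arm and show what could happen, not what is expected.

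The sponsor should correct this, but the trial's main result does not depend on it. The primary feasibility endpoints and the halting rule are untouched.

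**What to change.** **Preferred change.**

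- Delete the t-test sentence from 10.4.3 and 10.4.4.
- Report by arm the number and percentage of participants with each AE and, separately, the number of episodes.
- Use as denominator all randomised participants who took at least one dose, and add this to 10.3 as the safety set.
- Give the risk difference, fluoxetine minus placebo. A 95% score interval labelled descriptive is optional. For the assumed 6/23 v 1/20, the Miettinen-Nurminen interval around 21 points runs from −2 to 43.
- Report how many randomised participants have unknown dosing status or no safety contact after withdrawal. Section 5.4.2 promises only attempted phone contact and there is no early termination visit, so the all-dosed set may be incomplete.
- In 10.4.6, replace the tests with descriptive summaries by arm.

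**Alternative.** If the sponsor wants to keep an AE or baseline test, name it in 10.4.1 as an exception. For AEs, also state the tail, the counting unit, the all-dosed denominator and that the test is unadjusted for multiplicity (section 10.4.9 is marked not applicable).

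**Cost.** Wording only, with no new data collection. Under the preferred change, AEs and baseline variables carry no p-value.

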2.3.1 KNOWN POTENTIAL RISKS

Fluoxetine is a FDA approved antidepressant medicine which is used very frequently and safely. Some patients may experience some side effects that include: Nausea, diarrhea, anorexia, dry mouth, dyspepsia, insomnia, anxiety, nervousness, somnolence, tremor, decreased libido, abnormal dreams, headache, asthenia, flu like syndrome, fever, weight loss, Flatulence, constipation, rash, pruritus, abnormal vision etc. However, rare and serious side effects are also possible which include; worsening depression, increase suicidal thoughts or actions, mood swings, acting aggressive or violent, serotonin syndrome, severe allergic reaction- trouble breathing, swelling of face, tongue, eyes or mouth, rash, hives, abnormal bleeding if you are taking blood thinner coumadin warfarin (Coumadin®), a non-steroidal anti-inflammatory drugs (NSAIDs, like Ibuprofen or naproxen), or aspirin, increase in seizure frequency and possible irregular heart rhythm called Torsades de pointes due prolonged OT.

Fluoxetine is classified by FDA as category "C" for use in pregnancy which means there is a known risk of birth defect animal fetus but there are no adequate data and well-controlled studies in human. Stopping fluoxetine suddenly can cause serious symptoms including:

- Anxiety, irritability, high or low mood, feeling restless or changes in sleep habits
- Headache, sweating, nausea, dizziness
- Shaking, confusion etc

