5.4 PARTICIPANT WITHDRAWAL OR TERMINATION

5.4.1 REASONS FOR WITHDRAWAL OR TERMINATION

Participants are free to withdraw from participation in the study at any time upon request. An investigator may terminate participation in the study if:

- Any clinical serious adverse events related or unrelated to the study.
- The participant meets an exclusion criteria (either newly developed or not previously recognized) that precludes further participation.

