5.4.2 HANDLING OF PARTICIPANT WITHDRAWALS OR TERMINATION

If the participant withdraws or terminates participation in the study prior to randomization to one of the intervention arms, no attempt for follow up will be made.

If the participant withdraws or terminates participation in the study after randomization to one of the intervention, we will attempt to contact them via phone calls for safety follow up. No other outcome measures will be collected.

If the participant in the study develops serious adverse events (SAEs), they will be terminated from further participation in the study. They will be referred for appropriate evaluation and treatment (if already not being done). They will be followed up until resolution of the adverse events.

Version 01.2 Protocol:201607761 Version 20.2 Version 01.2

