8.1.2 DEFINITION OF SERIOUS ADVERSE EVENTS (SAE)

An AE or suspected adverse reaction is considered "serious" if, in the view of the investigator, it results in any of the following outcomes: death, a life-threatening adverse event, inpatient hospitalization or prolongation of existing hospitalization, a persistent or significant physical or mental incapacity including worsening depression, increase suicidal thoughts or actions, acting aggressive or violent, or a congenital anomaly/birth defect. Important medical events that may not result in death, be life-threatening, or require hospitalization may be considered serious when, based upon appropriate medical judgment, they may jeopardize the patient or subject and may require medical or surgical intervention to prevent one of the outcomes listed in this definition. Examples of such medical events include allergic reactions including angioedema of face, tongue, mouth, and bronchospasm requiring intensive treatment in an emergency room or at home, or increased seizure frequency from baseline that do not result in inpatient hospitalization.

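### No safety analysis set is defined; if the only named dataset, per protocol, is applied to the adverse event comparison, participants terminated for an SAE and other early stoppers would drop out of the compared frequencies

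*Combined protocol and SAP*

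**What the plan says.** Section 10.3 of the combined protocol and SAP consists of "Per protocol analysis". It gives no definition and no scope, and no safety, as-treated or all-randomised set appears elsewhere. Section 10.4.4 states "Frequency of each adverse events will be compared between the two groups" and adds a one-sided t-test at 0.025. The adverse event paragraph at the end of 10.4.3 repeats this. Neither names a population. Section 10.4.4 also asks for a table of serious treatment-emergent events and of events that led to stopping the drug early, without stating a denominator.

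On participants with an SAE, section 5.4.2 says that one who "develops serious adverse events (SAEs), they will be terminated from further participation in the study". Section 5.4.1 is softer: among the grounds on which the investigator may terminate participation it lists "Any clinical serious adverse events related or unrelated to the study". Under 5.4.2, SAE cases are followed until resolution, and safety phone calls are attempted for those who withdraw after randomisation. Section 4.1 collects adverse effects for every subject.

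The phrase per protocol has one other use in the analysis sections: 10.4.2 counts participants who completed the study per protocol. Section 5.3 recruits until each group has 20 completers.

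**The concern.** A per-protocol set restricted to completers selects participants partly on the outcome that an adverse event comparison measures. A participant whose event ends participation is removed from both the numerator and the denominator, and what remains is the experience of those who tolerated the drug.

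The events exposed to this matter in an epilepsy population. Section 2.3.1 lists "increase in seizure frequency and possible irregular heart rhythm" among the rare, serious effects of fluoxetine. Section 8.1.2 offers "increased seizure frequency from baseline that do not result in inpatient hospitalization" as an example of an event that may be judged serious, and its definition of incapacity extends to the group "including worsening depression, increase suicidal thoughts or actions". Early stoppers are also the people most directly exposed to the abrupt-withdrawal effects in 2.3.1, introduced by "Stopping fluoxetine suddenly can cause serious symptoms including".

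Section 10.1 describes the trial as a pilot that supplies estimates for later studies. What is at stake is whether its between-arm adverse event frequencies can serve that purpose. Participant protection is not at stake: the independent medical examiner receives every SAE (8.4.2), and the halting rule (8.5) counts reported events, not members of an analysis set. The recruitment and retention endpoints are unaffected.

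**Working it through.** The plan gives no adverse event rate, dropout rate or sample size calculation, so it has no figure to reproduce. The check is a reading of the text followed by an illustration.

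**Step 1: the text.**

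| Section | Content | Consequence |
|---|---|---|
| 10.3 | Per protocol is the only dataset | No other set is available to 10.4.3 or 10.4.4 |
| 10.4.2, 5.3 | Per protocol is linked to completing; target of 20 completers per group | Nearest available meaning is completers |
| 5.4.2 | SAE leads to termination | Not a completer, if the SAE comes before completion |
| 10.4.3, 10.4.4 | Frequencies compared by arm | Such a participant contributes no event and no denominator |

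**Step 2: SAEs that end participation.** Let 20 participants per arm complete and s further dosed participants be terminated for an SAE and replaced. The all-dosed frequency is s/(20 + s); the completer frequency is 0/20. The values of s are assumed, and the intervals are Clopper-Pearson 95%.

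| s | All dosed | Completers |
|---|---|---|
| 0 | 0/20 = 0% (0% to 16.8%) | 0/20 |
| 2 | 2/22 = 9.1% (1.1% to 29.2%) | 0/20 |
| 5 | 5/25 = 20.0% (6.8% to 40.7%) | 0/20 |

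The upper limit for 0/20 is 1 − 0.025^(1/20) = 16.8%. As a contrast between arms, 3 terminations on fluoxetine and 1 on placebo give 3/23 = 13.0% against 1/21 = 4.8% among all dosed, and 0/20 against 0/20 among completers.

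**Step 3: without replacement.** The summary randomises forty subjects, and 10.6.1 enrols 20 at each of two locations, 1:1. Both imply 20 randomised per arm. Then s = 2 gives 2/20 = 10.0% among all dosed and 0/18 among completers; s = 5 gives 5/20 = 25.0% and 0/15. The denominators change, but the direction does not.

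**Step 4: other adverse events.** Let a share w of dosed participants stop early because of a given event, let everyone else complete, and let completers have that event at rate c. The all-dosed rate is w + (1 − w)c, so the completer rate understates it by w + (1 − w)c − c = w(1 − c).

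- w = 5%, c = 40%: 0.05 × 0.60 = 3.0 percentage points
- w = 10%, c = 20%: 0.10 × 0.80 = 8.0 points
- w = 20%, c = 10%: 0.20 × 0.90 = 18.0 points

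The last line is extreme, since a fifth of an arm would have to stop for the same event.

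**The case against.** The strongest reply is that 10.3 was never meant to govern safety. It does not state its scope, and it cannot cover everything in section 10, because 10.4.2 reports percentages of all patients screened. Section 10.4.4 begins by recording all adverse events and ends with a table of SAEs and discontinuation events that could hardly be filled from completers. On this reading the population is unstated, and nobody planned to leave SAE cases out.

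The links in the chain are also loose. Per protocol is never defined. Section 5.4.1 makes termination discretionary where 5.4.2 makes it mandatory. Section 8.1.2 makes increased seizure frequency without hospitalisation serious only on medical judgment. An SAE during the taper, after the week 4 visit, might still count as occurring in a completer. The zero in Step 2 follows from equating per protocol with completers, the event counts are assumed, and 2.3.1 calls the serious drug effects rare.

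Most of this stands. A reader might infer that the plan excludes SAE cases from safety reporting, or that 10.3 binds every analysis in section 10. The documents support neither. The events are recorded, followed, sent to the independent medical examiner and tabulated.

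The reply does not supply a population for the comparison. Collecting events for all subjects settles what is recorded, not who is counted. The table has no stated set or denominator, and if it implies a wider set it conflicts with the only dataset that the plan names.

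**Conclusion.** The point holds in conditional form and is minor. No safety set is defined. If per protocol is applied to the adverse event comparison and means completers, participants terminated for an SAE before completion, and other early stoppers, would drop out of the compared frequencies and denominators. The bias would run toward apparent safety and would be larger in the arm with more event-related stopping.

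The size is illustrative only. With replacement, 2 of 22 or 5 of 25 dosed participants with a terminating SAE would show as 0 of 20; without it, 2 of 20 or 5 of 20 would show as 0 of 18 or 0 of 15. For other events the understatement is w(1 − c), or 3 to 18 points over the assumed values. These figures rest on the completer reading, on mandatory termination under 5.4.2, on SAEs arising before completion, and on assumed counts and rates.

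A reader might go further and conclude that the trial's safety results would hide serious harm. The documents do not support that, because the table in 10.4.4 keeps these events in the report. What could be distorted is the by-arm comparison and its denominators.

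**What to change.** In section 10.3, add a safety set: all randomised participants who took at least one dose, analysed by treatment received, with no exclusion for early stopping, SAE or protocol deviation. State that the adverse event comparison in 10.4.3 and 10.4.4, and the table of SAEs and discontinuation events, use this set. Define frequency as the number of participants with at least one event divided by the number in the safety set, by arm. Limit the per-protocol set to the HCVR and peri-ictal measures.

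The cost is SAP wording. Adverse events are already collected for all subjects, SAE cases are already followed to resolution, and 5.4.2 already provides for safety calls after withdrawal. The small downside is that early stoppers will have shorter or less complete adverse event follow-up than completers, which the report should state.
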